### 1.4 STUDY FLOW CHART COHORT 3 (FORGO VISIT 4 AND KEEP VISIT NUMBERING AS IN COHORT 1 AND 2)

#### STUDY FLOW CHART FOR COHORT 3 (forgo visit 4)

Phase	Screening	Treatment Period				Follow-up
	1	2	3	4	5 (EOT)	6 (EOS)
VISIT	1	2	3	4	5 (EOT)	6 (EOS)
Day	D-21 to D-1 a	D1	Between D6 and D8	Forgo	D14+/-1 b	Between D26 and D30
Informed consent c	X					
Discharge c	<-----X----->					
IRT contact	X	X			X	X
Visit at clinical site d		X	X e		X e	X
Phone check/Visit at clinical site g						X
Inclusion/exclusion criteria	X	X				
Medical/surgical history	X					
Prior/concomitant medications	<-----X----->					
Randomization h		X				
Meal i		X	X		X	
Diary j (daily): IMP intake, concomitant medications, AE BP k		X	<-----X----->			
Study treatment administrationl						
IMP dispensing		X				
IMP administration	<-----X----->					
 I-albumin injection (for plasma volume assessment)		X			X	
Deuterium oxide intake (for total body water assessment)		X			X	
Safety						
Physical examination m	X	X			X	
Height	X					
Body weight n	X	X			X	
Echocardiogram o	X					
Vital signs f , ECG p	X	X	X		X	
Body temperature q	X	X			X	
Hematology r	X	X t			X t	
Biochemistry s	X	X t	X		X t	
Liver function (AST, ALT, ALP, GGT, total and conjugated bilirubin)	X	X	X		X	
Urine (Lab)		X	X		X	

Phase	Screening	Treatment Period				Follow-up
		1	2	3	4	
VISIT	1	2	3	4	5 (EOT)	6 (EOS)
Day	D-21 to D-1a	D1	Between D6 and D8	Forgo	D14+/-1b	Between D26 and D30
β-HCG blood test U	X				X	
Plasma FSH U	X					
Adverse event collection	<-----X----->					
Pharmacodynamics						
Blood collection for hemoconcentration samples V		X			X	
Blood collection for  I-albumin		X			X	
Blood collection for deuterium oxide		X			X	
Uric acid		X			X	
Erythropoietin		X			X	
NT-proBNP		X			X	
Beta-hydroxybutyrate		X			X	

- a* The laboratory evaluation closest to D1 will be used as the screening lab in case of discrepancies with prior labs. Oral hypoglycemic drugs and long-acting insulin should not be administered the morning of D1 or D14. If appropriate (for example, for patients admitted in the early morning hours), screening procedures may also take place on D1.
- b* Sites should adhere to D14 whenever possible
- c* Occasionally, a patient might be admitted, screened and randomized on the same day. In those cases, informed consent will also be sought during that day. In other cases, randomization may take place before discharge from hospital or admitting unit. If discharge is before D1, then the patient will come back to the site at D1 (Visit 2) for Randomization and IMP dispensing. For hospitalized patients eligible for discharge on study day D1, the timing of discharge is at the discretion of the treating physician but should not be less than 6 hours following administration of study drug. Patients that are not eligible for discharge, may complete all or part of the study as inpatients (hospital or other appropriate unit).
- d* Those visits need not be in an outpatient setting. For example, where mobility issues might cause restrictions, or patient is in a step-down unit or rehabilitation ward, the Investigator or designee could perform the Visit and relevant assessments and collect blood or urine samples at that setting. Visit 6 is the end of study visit (EOS). All patients will have a phone check at EOS. Patients may return to the clinical site if, in the judgment of the Investigator, may require a physical examination and additional investigations. A telephone call may also be scheduled soon after the End of Treatment Visit 5.
- e* IMP accountability and compliance check performed at end of treatment (EOT) Visit 5 and on visits planned at clinical site (Visit 3 )
- f* Vital signs: including heart rate, systolic and diastolic blood pressure measured after 10 minutes in supine or sitting (preferably sitting) resting position. Orthostatic changes in blood pressure will be assessed once for all patients not limited by mobility issues (assess BP when supine or sitting for 10 mins and after 3 mins standing). For patients returning to the day unit for D1, they should stay in the unit. Their vital signs will be assessed at baseline and every 2 hours after administration of IMP. Patients should be monitored for at least 6 hours prior to discharge from the unit.
- g* Phone check will be to record any adverse events that occurred after study drug discontinuation, and to record daily BP readings since EOT Visit 5. Patients may return for a further visit (Visit 6) if in the opinion of the investigator they need a follow up examination and/or investigations.
- h* IRT contact for screening/randomization. Randomization within 7 days of discontinuation of IV diuretic therapy.
- i* Meals should be taken approximately 15 min after IMP administration throughout the study. On study day Visits 2 and 5, and Visits 3, , patients should fast for approximately 6 hours prior to IMP administration.
- j* Diary dispensed on D1 (Visit 2). The diary will be reviewed and information recorded on eCRF. If the last follow up is by phone check, all relevant information will be captured and transcribed to the eCRF. Patients who may need to remain inpatients for some or all of the visits will also receive a diary. While inpatients, relevant data such as AE and IMP intake will be entered into the diary. For inpatients, BP and concomitant medications will be recorded in the patient source documents. Those who become eligible for discharge will also receive BP monitors and continue with diary updates on a daily basis.
- k* Patients will be taught how to perform the automated BP readings. Automated BP readings will be performed in triplicate, between 6 AM to 10 AM on a daily basis, starting D2 and ending at the last post-study follow up.
- l* Study treatment ends on Day 14 (EOT).

- m* Physical examination includes at a minimum: heart and respiratory auscultation; peripheral arterial pulse; pupil, and abdomen examination. All physical examinations in diabetic patients, including abbreviated physical examinations, will include examination of the lower extremities to evaluate for any evidence of foot ulcers or infection should be performed as part of the general physical examination and this examination should be documented on the e-CRF.
- n* All body weight measurements on scale provided by site staff.
- o* All patients must have a documented echocardiogram, either performed during current admission or within 12 months from the index hospitalization.
- p* ECG at Visit 2, Visit 3 and Visit 5 (EOT) only.
- q* Oral or tympanic body temperature.
- r* Complete blood count / hematocrit / hemoglobin.
- s* Creatinine, urea, electrolytes.
- t* For Visits 2 (Day 1) and 5 (Day 14±1), those samples will be obtained as part of the Hemoconcentration sampling, thus no additional samples for Hematology or Biochemistry are required. It is indicated here as a reminder that baseline hematology and biochemistry is done on Visits 2 and 5. For all other Visits, Hematology and Biochemistry samples are to be obtained as indicated.
- u* Beta-HCG test will be for all women of child-bearing potential as defined in the inclusion/exclusion criteria, and FSH to assess menopausal status when necessary.
- v* Hemoconcentration is determined by measurement of hematocrit, hemoglobin, albumin and total protein. Baseline biochemistry (creatinine, urea and electrolytes) and hematology (CBC) is also determined from those samples.

**1.5 PERIOD FLOW CHART (COHORT 3)**

VISIT	VISIT 2 and VISIT 5											VISIT 3	
Day	D1 and D14(+/- 1 day) a											Between Day 6 and Day 8	
Time (hour/minute)	-3H	-2.5H	-2H	-1H	0H	0.5H	1H	3H	4H	5H	6H	-2.5 H	0H
Indicative clock time	7 am	7:30am	8 am	9:00 am	10 am	10:30am	11 am	1 pm	2 pm	3 pm	4 pm		
Discharge b											X		
Concomitant medications													
Randomization c	X												
IMP accountability and compliance							X						
Inclusion/Exclusion criteria c	X												
Meal e					X								X
Semi-recumbent position				X									
Study treatment administration													
IMP administration					X								X
 I-albumin injection				X									
Deuterium oxide intake f		X											
Safety													
Physical examination	X												
Vital signs	X							X g				X	
Body weight o	X												
ECG	X											X	
Urine (lab)		X										X	
Hematology				X h									
Biochemistry				X h								X	
β-HCG i		X											
Liver function (AST,ALT, ALP, GGT, total and conjugated bilirubin) j			X									X	
Adverse event collection								X					

VISIT	VISIT 2 and VISIT 5											VISIT 3	
Day	D1 and D14(+/- 1 day) a											Between Day 6 and Day 8	
Time (hour/minute)	-3H	-2.5H	-2H	-1H	0H	0.5H	1H	3H	4H	5H	6H	-2.5 H	0H
Indicative clock time	7 am	7:30am	8 am	9:00 am	10 am	10:30am	11 am	1 pm	2 pm	3 pm	4 pm		
Pharmacokineticsk													
Pharmacodynamics													
Blood collection Hemoconcentration, l				X									
Blood collection for  I-albumin				X m									
Blood collection for deuterium oxide n		X					X						
Uric acid		X											
Erythropoietin		X											
NT-ProBNP		X											
Beta-hydroxybutyrate		X											

- a Sites should adhere to D14 whenever possible
- b For hospitalized patients eligible for discharge on study day D1, the timing of discharge from the hospital is at the discretion of the treating physician but should not be less than 6 hours following the administration of study drug. Patients that are not eligible for discharge, may complete all or part of the study as inpatients (hospital or other appropriate unit). For patients returning to the day unit for D1, they should also stay in the unit and have their vital signs assessed every 2 hours after IMP administration and discharged not sooner than 6 hours after IMP administration. Laboratory tests may be performed in the hospital or outpatient unit, depending on whether the patient remains hospitalized.
- c Day 1 only. IRT contact for randomization. The time is indicative, as randomization should take place after review of inclusion/exclusion criteria
- e Meal to be taken within 15 minutes after administration of study drug.
- f Deuterium oxide intake should take place after blood collection for baseline measurements.
- g Vital signs: including heart rate, systolic and diastolic blood pressure measured after 10 minutes in supine or sitting (preferably sitting) resting position. Orthostatic changes in blood pressure will be assessed once for all patients not limited by mobility issues (assess BP when supine or sitting for 10 mins and after 3 mins standing). For patients returning to the day unit for D1, they should stay in the unit. Their vital signs will be assessed at baseline and every 2 hours after administration of IMP. Patients should be monitored for at least 6 hours prior to discharge from the unit.
- h For Visits 2 (Day 1) and 5 (Day 14±1), those samples will be obtained as part of the Hemoconcentration sampling, thus no additional samples for Hematology or Biochemistry are required. It is indicated here as a reminder that baseline hematology and biochemistry is done on Visits 2 and 5. For all other Visits, Hematology and Biochemistry samples are to be obtained as indicated.
- i β-HCG performed at screening and D14 only
- j Indicative time. Those samples can be obtained at the same time as the other samples are collected, eg, biochemistry.
- k Pharmacokinetic samples will not be collected for cohort 3.
- l Hemoconcentration is determined using the following: Hematocrit, hemoglobin, total protein and albumin. Baseline biochemistry (creatinine, urea, electrolytes) and complete blood count will also be determined from those samples
- m One sample will be collected just before injection of I-albumin (-1H, PD00) and further sample collection will start 12 min following the injection. Samples will then be collected every 6 minutes starting – 0H48 min: -0H48 min(PD01), -0H42min(PD02), -0H36min(PD03), -0H30min(PD04), -0H24min(PD05) min. For blood collection on D14 sample notation should be: -1H (PD06), -0H48min (PD07), -0H42min (PD08), -0H36min(PD09), -0H30min(PD10), -0H24min(PD11)

- n Following administration of deuterium oxide, blood collection on D1: At -2.5H (PY00), 1H (PY01), and on Day 14: At -2.5H (PY02), 1H (PY03)
  - o All body weight measurements on scale provided by site staff
- 

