### 6.2 DURATION OF STUDY PARTICIPATION

#### 6.2.1 Duration of study participation for each subject

- Screening period will be up to 21 days
- Treatment period is 14 ± 1 days
- Follow up period will be 14 ± 2 days
- Total study duration will approximately be 26-51 days

However, subject participation could be prolonged in case of safety concerns (see [Section 11.3.1](#)).

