### 8.3 EXCLUSION CRITERIA

- E 01. History of Type 1 diabetes mellitus
- E 02. Appears unlikely or unable to participate in the required study procedures, as assessed by the study Investigator, study coordinator, or designee (ex: clinically-significant psychiatric, addictive, or neurological disease), or sectioned due to an official or court order
- E 03. Tachyarrhythmia with ventricular rate  $> 130$  bpm at screening, unless determined to be clinically stable by the investigator current admission for worsening heart failure primarily triggered by causes such as acute coronary syndrome, pulmonary embolism, cerebrovascular accident, heart valve disorders (such as severe aortic stenosis), as determined by the Investigator

- E 04. Clinically significant myocardial infarction (MI) within past 1 month as determined by Investigator and with objective evidence from ECG, and/or cardiac imaging and/or coronary angiography. Small isolated elevations in troponin that often accompany HF hospitalization are not an exclusion, nor are clinically significant MIs that have been re-vascularized without complications
- E 05. Patients who recently had or scheduled to have cardiac interventions may be eligible if:
- Stable 48 hours post procedure AND
  - Have diuretic treatment planned for the duration of treatment in this study
- E 06. Current use of or recent suspension of digoxin therapy with high levels of digoxin (level should be obtained and must be <1.2 ng/mL) at screening.
- E 07. History of heart or kidney transplant
- E 08. Diagnosis of hypertrophic obstructive cardiomyopathy
- E 09. End-stage HF defined as requiring left ventricular assist device insertion, intra-aortic balloon placement (IABP), or any type of mechanical support during the study period
- E 10. Pregnancy (demonstrated by serum pregnancy test at screening), breast-feeding, or inability or refusal to undergo pregnancy testing
- E 11. Use of any investigational drug(s) or prohibited therapy or sodium-glucose co-transporter 2 (SGLT2) inhibitor 5 half-lives prior to screening
- E 12. Patients with moderate or severe respiratory, hepatic, neurological, psychiatric, active malignant tumor or other major systemic disease (including any diseases with evidence of malabsorption), making implementation of the protocol and/or the interpretation of the study results difficult

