#### 13.1.1 Screening procedures

Patients will undergo Screening assessments at Visit 1 (Day -21 to Day -1, and up to randomization on D1, to allow, for example, cases where the patient may be admitted and likely to be discharged on the same day) following signing of the informed consent form. The patient will receive information on the study objectives and procedures from the Investigator. The patient will have to sign the informed consent prior to any action related to the study.

The interactive response technology system (IRT) will be contacted at Visit 1 for notification of Screening Visit and to obtain the patient identification number.

Screening will include the investigations listed in the Study Flow Chart ([Section 1.2](#)) and detailed in [Section 10.2](#).

All patients must have a documented echocardiogram, either performed during Visit 1 or within 12 months from current admission or screening.

Rechecking of any parameters at screening is subject to the Investigator's judgment, allowed once.

Patients who meet all the inclusion criteria and none of the exclusion criteria will be eligible for randomization.

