#### 13.1.2 Inclusion procedures

Inclusion procedures will be carried out during Screening (D-21 to D-1) or D1, as appropriate for each patient. Those will include the investigations listed in the study flow chart ([Section 1.2](#)) and detailed in [Section 10.2](#).

Baseline parameters may be rechecked once, at the Investigator's discretion. Results of a rechecked value should be known before the inclusion. The last value should be considered as the baseline value and reported in the case report form.

Prior to final inclusion and randomization, all patients must have completed the last planned IV administration (bolus or infusion), and *either* have commenced oral diuretic therapy *or* have a clear and documented plan to commence oral diuretic therapy. Patients may be discharged and return for Day 1 procedures within seven (7) days from discontinuation of IV diuretic administration.

Final inclusion and randomization, as appropriate, will be performed just before commencement of procedures on Day 1. Each patient will receive an incremental identification number corresponding to his/her order of enrollment in the study.

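### In the visible text, a woman screened before Day 1 needs no repeat pregnancy test before her first 131I-albumin injection and first study dose

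*Protocol*

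**What the plan says.** **When the test is done.** The study flow charts (Protocol Section 1.2 for cohorts 1 and 2, Section 1.4 for cohort 3) mark the beta-HCG blood test at Visit 1 and Visit 5 and leave Visit 2 blank. Footnote i to both period flow charts (Sections 1.3 and 1.5) says the test is "performed at screening and D14 only". SAP Appendices A and B repeat this schedule.

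**What the exclusion rests on.** E 10 in Section 8.3 defines the pregnancy exclusion by the screening result: "Pregnancy (demonstrated by serum pregnancy test at screening".

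**How old that result can be.** Section 6.2.1: "Screening period will be up to 21 days". Section 1.4, footnote h: "Randomization within 7 days of discontinuation of IV diuretic therapy". Footnote a to the same chart adds that, where appropriate, "screening procedures may also take place on D1".

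**Rechecks and the Day 1 eligibility check.** Section 13.1.1: "Rechecking of any parameters at screening is subject to" the Investigator's judgment, and is allowed once. Section 13.1.2: "Baseline parameters may be rechecked once", again at the Investigator's discretion. Section 9.4 asks the site to confirm all criteria before randomizing on Day 1, and footnote c in Section 1.5 says "randomization should take place after review of inclusion/exclusion criteria".

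**The concern.** Day 1 brings the first exposure to an investigational drug and, at sites that can perform it and unless the patient declines, to a radioactive tracer. The Day 1 eligibility check covers E 10, but the only evidence that the schedule supplies for it is the screening test. A pregnancy that began, or became detectable, after that test would go unnoticed until Visit 5.

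By then the treatment course is nearly over. With Visit 5 on Day 14, the woman has already taken 13 of 14 doses and, where the tracer is used, received one injection of up to 25 µCi. Sections 11.2.3 and 12.1 require study drug to stop once pregnancy is known, but on this schedule that would spare one dose. A Day 1 test would find such a pregnancy before any exposure. It would not detect conception during treatment; contraception under I 05 and the Visit 5 test address that.

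**Working it through.** No figure in the plan rests on this point. The check compares the places that schedule a pregnancy test and then derives the age of the result from the visit days.

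**Step 1. Is any Day 1 test required?**
- Study flow charts: marks at Visits 1 and 5 only.
- Period flow charts: the mark at -2.5H sits in a column shared by Visits 2 and 5. Footnote i removes it from Day 1.
- Section 10.2.1, item 7: names a serum test for women of childbearing potential but gives no day, so the charts govern.
- Table 12 (Section 10.5): at most 2 samples for beta-HCG or FSH, which fits screening plus Visit 5.
- Sections 9.4, 13.1.1 and 13.1.2: a check of criteria and a permitted recheck. Neither requires a repeat test.

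The visible text therefore requires no test between screening and the Day 1 procedures, unless screening is itself on Day 1.

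**Step 2. How old can the screening result be at first dose?**
Let r be the days of IV diuretics remaining after the screening test. Randomization follows within 7 days of stopping, and screening starts no earlier than D-21. With no Day 0, D-21 to D1 is 21 days. So:

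maximum age = min(r + 7, 21) days

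The documents do not give r. The values below are assumptions that show the range.

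| Case | Calculation | Maximum age |
|---|---|---|
| Screened on Day 1 | – | 0 days |
| r = 0 | 0 + 7 | 7 days |
| r = 3 | 3 + 7 | 10 days |
| r = 5 | 5 + 7 | 12 days |
| r = 14 | 14 + 7 | 21 days (the cap) |

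**Step 3. Exposure before the next scheduled test.**
With Visit 5 on Day 14, doses on D1 to D13 come first: 13. The ±1 day window makes this 12 to 14.

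**Step 4. Where must a Day 1 test fall?**
The period chart places randomization at -3H, deuterium oxide at -2.5H, the tracer at -1H and the dose at 0H. Sections 10.1.2.1 and 10.1.2.2 place deuterium oxide immediately after the baseline specimens. Section 13.1.2 places final inclusion and randomization just before Day 1 procedures begin. A test drawn at -2.5H would come after randomization, and deuterium oxide could be taken before the result. The test therefore has to be done on arrival. Footnote c to the period chart treats the randomization time as indicative, so waiting for a result is compatible with the protocol.

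**Step 5. Blood volume if serum is used.**
The current row is 2 × 3.5 = 7 mL, which matches the difference between the female and male totals (184.5 − 177.5 = 7). With one more sample:
- row: 3 × 3.5 = 10.5 mL
- female total: 184.5 + 3.5 = 188.0 mL
- cohort 3, without the 14 mL of pharmacokinetic samples: 184.5 − 14 + 3.5 = 174.0 mL

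**The case against.** The strongest reply is that the most relevant content cannot be seen. Appendix A carries decision-tree figures on contraception and pregnancy testing, and Section 18 makes the appendices part of the protocol. Those figures may call for a pre-dose test. This stands, and it limits the claim to the visible text. It does not remove the need for a change: footnote i says the test is done at two times only and E 10 names screening alone, so both would conflict with such a figure.

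Second, controls already exist. Eligibility is checked again on Day 1, a recheck is permitted, footnote a lets the laboratory result closest to Day 1 prevail over discrepant earlier ones, and I 05 requires double contraception during the study. A careful site could retest and act on the result. That is fair, but it describes what a site may do. A site that follows the schedule exactly does not retest, and contraception during the study cannot exclude a conception shortly before screening that was not yet detectable.

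Third, the yield is not shown. The documents give neither the number of women of childbearing potential nor the days of IV treatment remaining after screening, and cohort 3 has only about 34 patients. This also stands. The case rests on the low cost of the test and the avoidable nature of the exposure, not on an expected count of pregnancies.

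**Conclusion.** The point holds for the visible text: when screening precedes Day 1, no repeat pregnancy test is required before the first tracer injection and first dose. The size of the gap is as tabulated, from 0 days to the cap of 21. The intermediate values rest on assumed days of remaining IV treatment. The number of women affected is unstated and probably small, and nothing in the sample size, power or analysis changes.

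A reader might infer more, and the documents do not support it. They do not allow dosing without any pregnancy test, because a serum test at screening is required for women of childbearing potential. They do not suggest that three-week-old results are usual: the 7-day rule means that a 21-day gap needs 14 further days of IV diuretics after screening. Nor can one conclude that the whole protocol lacks a pre-dose test while the Appendix A figures are unseen. This is a cheap safety improvement to the schedule, not a flaw in the trial's inference.

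**What to change.** Make the change in the cohort 3 charts (Sections 1.4 and 1.5). For women of childbearing potential not screened on Day 1:

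- Require a rapid hCG test on arrival on Day 1, with a negative result before IRT randomization. This keeps the order in Section 13.1.2 and places the result before deuterium oxide, 131I-albumin and study drug. A positive result becomes a screen failure.
- Add Day 1 to footnote i, mark Visit 2 in the Section 1.4 chart, and extend E 10 to screening and Day 1 in both Section 8.3 and the synopsis.
- If urine is used, specify a device that reads hCG only, since Section 10.7 tells sites not to run unblinded urine analyses, and widen Section 10.2.1, item 7, which names serum.
- If serum is used, change Table 12 to a maximum of 3 samples (10.5 mL) and the female total to 188.0 mL, or 174.0 mL in cohort 3.
- Check the Appendix A decision trees against the revised schedule.

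The cost is one rapid test per woman concerned, 3.5 mL more blood if serum is chosen, and possibly a short delay that morning. It falls on the 1 to 3 US centers running cohort 3.
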